3.4.2.1 Description

We will describe at each visit, globally and by age classes at inclusion ([6-9[months, [9-12] months):

- proportion of measles vaccine dose 1,
- proportion of measles vaccine dose 2,
- proportion of patients of at least one additional dose of measles vaccine.

For children included at [6-9[months old, measles vaccine dose 1 is supposed to be administered before the first follow-up visit (i.e V1) occurring 4 months after inclusion (i.e M4); measles vaccine dose 2 is supposed to be administered before V2 (M8) if included at [7-9[months old or before V3 (M12) if included at [6-7[months old.

For children included at [9-12] months old, measles vaccine dose 1 is supposed to be administered before inclusion, and measles vaccine dose 2 is supposed to be administered before V1 (M4) if included at [11-12] months old or before V2 (M8) if included at [9-11[months old.

3.4.2.2 Main analysis first intention:

In first intention, analysis will be conducted at the individual level, adjusting for clustering.

A time-to-event approach will be used, where time is defined from inclusion to the first occurrence of an additional dose of measles vaccine. A shared frailty model (Cox proportional hazards model with a random intercept for cluster)^{16,17} will be used to estimate the effect of the intervention.

The intervention effect will be estimated as a hazard ratio (HR) with 95% confidence intervals, comparing the instantaneous risk of receiving an additional dose of measles vaccine between the intervention and control arm, accounting for clustering via the shared frailty term.

For interpretability, the cumulative incidence of vaccination at 12 months will be estimated from the shared frailty Cox model and reported by study arm, together with the absolute difference between arms. Kaplan–Meier curves will be used for descriptive visualization only.

This approach appropriately accounts for clustering, the timing of vaccination, and censoring, and provides a statistically valid and clinically interpretable estimate of the intervention effect.

No adjustment for baseline vaccination status is planned, as the expected number of doses depends on age at inclusion (for children aged 6–9 months at inclusion, 0 dose is expected).

The variance of the shared frailty term will be reported to describe the between-cluster variability.

Adjusted analyses

A shared frailty Cox proportional hazards model will be re-run after adjustment on a selection of baseline covariates, with additional variables selected by the results of the qualitative survey.

We will adjust on the following individual baseline covariates:

- Age at inclusion (to account for differences in vaccination eligibility at baseline) ;
- Mother's age;
- Study level;
- Number of children in the family;
- Distance of home from health facility;
- Level of food insecurity.

And on the following cluster baseline covariates:

- Number of days with no cold chain
- Number of days of stock of measles vaccines

Handling of missing data / censoring

All available data will be used for the primary analysis. Children lost to follow-up or who died before receiving an additional dose will be censored at the last available visit or date of death, respectively. Sensitivity analyses accounting for potential competing risks may be performed if the number of deaths is non-negligible.

In addition, we will perform sensitivity analyses to assess the potential impact of missing data (for children loss-to-follow-up before additional vaccination) on the study conclusions¹⁸. We will start by re-running the Model described above under the following two most extreme scenarios:

- Extreme scenario 1 ('worst' case for intervention): all censored patients in the NutriVax arm are assumed as failure (no additional dose of measles vaccine), and all censored patients in the control arm are assumed as success (at least one additional dose of measles vaccine).
- Extreme scenario 2 ('best' case for intervention): all censored patients in the NutriVax arm are assumed as success (at least one additional dose of measles vaccine), and all censored patients in the control arm are assumed as failure (no additional dose of measles vaccine).

We will check whether the study conclusion changes as indicated by the resulting p-values. In the case where both extremes result in the same statistical significance as the main analysis, no further tipping point analysis will be performed. In case the conclusions disagree, we will perform a tipping point search by identifying combinations where the level of significance switches from significant to non-significant (or vice versa) as described by Yan et al.¹⁹

3.4.2.3 *Main analysis second intention:*

In second intention, in case the model does not converge due to low numbers of clusters, we will use the cluster-level analysis. Individual data will be aggregated by cluster, and cluster-level summary statistics (e.g., cumulative incidence of vaccination at 12 months or median time to event) will be calculated. Intervention effects will then be compared between arms using appropriate statistical tests (Student's t-test or Wilcoxon rank-sum test), depending on the distribution of cluster-level summaries.

Assumptions will be verified and alternative approach will be considered in case assumptions are not met.

3.4.2.4 *Additional analyses :*

For completeness, the following additional analyses will be performed to provide descriptive and exploratory insights, without challenging the primary time-to-event results:

3.4.2.4.1 Binary end-of-follow-up analysis

A simple binary analysis of the event at the end of follow-up (yes/no) will be conducted as a sensitivity analysis.

Analysis using an individual-level analysis approach, using a logistic regression with random effects (a member of the family of generalised linear mixed model GLMM) with:

- a binary distribution (we analyse the change in the endpoint at individual level at the end of the follow-up)
- a logit link function;
- study arm as fixed effect;
- ward (cluster) as random intercept term.

No patient-level random effect will be included, as the endpoint is observed once per patient.

The intervention effect will be estimated as the cluster-specific odds ratio (OR) (with 95% CI) of vaccine between the intervention and the control arm.

We won't adjust for the baseline value because the number of doses expected depends on the inclusion age. For children aged 6-9 months at inclusion, it is normal to have 0 dose at inclusion.

Because this analysis uses only a single measurement per patient and does not account for the timing of vaccination or censoring, it has limited statistical efficiency. Differences with the primary time-to-event analysis may occur, but such discordances are expected and do not affect the primary conclusions.

3.4.2.4.2 Longitudinal repeated binary GLMM

A longitudinal repeated binary analysis of vaccination status at each follow-up visit will be conducted as a secondary exploratory analysis. This analysis is intended to provide additional insights into the evolution of vaccination probability over time, without replacing or challenging the primary time-to-event analysis.

Analysis will use an individual-level generalized linear mixed model (GLMM) with:

- a binary distribution
- a logit link function
- study arm as a fixed effect
- random intercepts for cluster (ward) and patient to account for clustering and repeated measurements within individuals.

Because the outcome is irreversible (once a child receives an additional dose, they remain “event positive” in subsequent visits), the intra-individual correlation (IAC) is largely absorbed by the monotonic outcome pattern, which may limit model identifiability and reduce statistical efficiency.

The intervention effect will be estimated as a ***cluster-specific odds ratio (OR)*** with 95% confidence intervals, derived from the GLMM.

This analysis differs from the binary end-of-follow-up sensitivity analysis, which does not include a patient-level random effect and focuses on robustness of the primary results. Differences with the primary time-to-event analysis may occur, but such discordances are expected and do not affect the primary conclusions.

3.4.3 Analysis of secondary endpoints:

3.4.3.1 *Anthropometric endpoints:*

We will analyse anthropometrics parameters mean change in children included in the longitudinal follow-up survey: MUAC, z scores for MUAC for age, weight/length for age, weight for weight/length, and height for age, as follow.

We will describe evolution at each visit of each parameter. And also, the evolution in absolute change at each visit of each parameter compared to the baseline measure.

In first intention, analysis will be conducted at the individual level, adjusting for clustering.

Analysis using an individual-level analysis approach, using a mixed effects linear regression with:

- a normal distribution,
- an identity link function,

- study arm as fixed effect,
- ward (cluster) as random intercept term,
- random intercept to account for within-individual correlation nested inside ward over time.

This model will be for the change in the endpoint of interest at different timing with baseline value.

The intervention effect will be estimated as the difference of means of delta (with 95% CI) between the intervention and the control arm.

The Kenward-Rodger correction¹¹ will be applied to estimate the number of degrees of freedom as it has been shown to improve estimation with a small number of clusters^{12–14}.

We will adjust by individual baseline parameter estimate and by cluster baseline mean parameter estimate.^{14,20}

Assumptions will be verified and alternative approach will be considered in case assumptions are not met.

In case of non-normal distribution of the endpoint, categorization into classes will be considered. If the outcome is binary, we will use logistic regression with random effects; if the outcome is a nominal with more than two classes, we will fit multinomial model with random effects^{10,21}, or we will keep continuous data using a transformation or a generalized additive mixed model GAMM^{22,23}.

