The original Statistical Analysis Plan planned an individual-level longitudinal mixed-effects logistic regression without a random effect at the patient level, thus not accounting for within-subject correlation that was anticipated in the sample size calculation. Even if a patient-level random effect were introduced, the outcome corresponds to an irreversible event (first additional dose of measles vaccine), resulting in a monotonic outcome pattern over time. In this context, the intra-individual correlation is largely non-identifiable, limiting the interpretability and appropriateness of a longitudinal binary GLMM.

Therefore, the primary analysis will use a time-to-event approach, with time since inclusion as the time scale and a shared frailty term for clusters. This approach provides a statistically valid and clinically interpretable estimate of the intervention effect while appropriately accounting for clustering and censoring.

The time-to-event analysis allows a more informative assessment of the intervention effect by incorporating the timing of vaccination, while preserving the original study objective of improving measles vaccine coverage during follow-up.

For completeness, the following additional analyses will be performed:

- A binary end-of-follow-up analysis (event yes/no at the end of follow-up) will be conducted as a sensitivity analysis for descriptive purposes only.
- A longitudinal repeated binary GLMM with a patient-level random effect will be conducted as a secondary exploratory analysis, acknowledging that the intra-individual correlation is largely absorbed by the monotonic outcome pattern.

These additional analyses are not intended to challenge the conclusions drawn from the primary time-to-event analysis.

This approach ensures consistency between the study design and the statistical methods, while preserving the study objectives, endpoints, and sample size assumptions. The original sample size calculation was based on the cumulative incidence of vaccination during follow-up. The time-to-event analysis targets the same cumulative process while using additional information on the timing of vaccination, and therefore does not compromise statistical power.

This amended Statistical Analysis Plan was finalised prior to database lock and before any comparative analysis was conducted.

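### The exploratory repeated-visit GLMM (SAP 3.4.2.4.2) labels as cluster-specific an odds ratio that is conditional on the child as well, and it has no time term although it is meant to show change over time

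*SAP*

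**What the plan says.** SAP 3.4.2 makes a shared-frailty Cox model the main analysis of the longitudinal endpoint (first additional measles dose after inclusion). It explains that a repeated binary model fits this endpoint badly, because the outcome cannot reverse and so "the intra-individual correlation is largely non-identifiable, limiting the interpretability and appropriateness of a longitudinal binary GLMM". The same section keeps such a model as a secondary exploratory analysis.

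SAP 3.4.2.4.2 then specifies that model: binary distribution, logit link, "study arm as a fixed effect", and "random intercepts for cluster (ward) and patient to account for clustering and repeated measurements within individuals". No visit or time term is listed. The analysis is "intended to provide additional insights into the evolution of vaccination probability over time". Its output is named as follows: "The intervention effect will be estimated as a *cluster-specific odds ratio (OR)* with 95% confidence intervals, derived from the GLMM".

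SAP 3.4.2.4.1 gives the same name to the odds ratio of a different model, fitted once per child at the end of follow-up with a ward intercept and no child intercept.

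The limitation that 3.4.2.4.2 admits is that the monotone outcome absorbs the within-child correlation, "which may limit model identifiability and reduce statistical efficiency". SAP 2.4 allows SAS or R. No section fixes the integration method for this model.

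**The concern.** Under a logit link, a regression coefficient is conditional on every random effect in the model. With ward and child intercepts, the arm effect compares children who share both the ward effect and the child effect. Only the 3.4.2.4.1 model gives an odds ratio conditional on the ward alone.

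The gap is large here because the outcome is permanent. A child vaccinated before M4 contributes yes, yes, yes; a child never vaccinated contributes no, no, no. Responses within a child are highly concordant, so the fitted child variance is large and the conditional log odds ratio is stretched with it.

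If the plan is followed as written, the report will hold two odds ratios with one name, for the same children and endpoint, that differ markedly in size. Nothing in the plan tells a reader that they answer different questions. In addition, a model without a time term cannot describe how the probability of vaccination evolves, which is its stated purpose.

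**Working it through.** **Inputs from the SAP.** 30% coverage and a 10-point difference, ICC 0.2, individual autocorrelation 0.5, power 80%, two-sided alpha 5%, 5% unusable data (1.8.2, 2.3.2); 20 wards allocated 1:1 (1.6, 1.7); visits at M4, M8 and M12 (3.4.2.1).

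**Assumptions.** Constant hazard over 12 months; coverage pairs above 30% vs 40%; ward SD on the logit scale; cluster autocorrelation of 1 in step 1.

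**1. The plan's own figure.** The SAP gives no value for this odds ratio, but its sample size can be checked. With m children per ward:

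Var = [p0(1−p0) + p1(1−p1)] × [1 + (m−1)ICC] × (1 − r²) / (10m), where r = [m·ICC + (1−ICC)·0.5] / [1 + (m−1)ICC].

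For m = 28: 0.21 + 0.24 = 0.45; 1 + 27 × 0.2 = 6.4; r = (5.6 + 0.4)/6.4 = 0.9375; Var = 0.45 × 6.4 × (1 − 0.8789)/280 = 0.001246. Then 0.10/√0.001246 − 1.96 = 0.87, a power of 80.9% (79.5% at m = 27). 28/0.95 rounds up to 30 per ward, 600 in all, as stated. The planning values are therefore coherent and are used below.

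**2. The model as written, large-sample fit.** Arm-only fixed effect, child intercept, ward effect omitted, 4001-point integration. Under a constant hazard the cumulative proportions at M4/M8/M12 are 1 − (1−p)^(1/3), 1 − (1−p)^(2/3) and p. For 30% vs 40% these are 11/21/30% and 16/29/40%. The model is fitted to the four possible patterns 000, 001, 011 and 111.

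| M12 coverage | End-of-follow-up log OR | Child-intercept log OR | Ratio |
|---|---|---|---|
| 30% vs 40% | 0.44 (OR 1.56) | 1.07 (OR 2.91) | 2.4 |
| 50% vs 60% (assumed) | 0.41 | 0.78 | 1.9 |
| 60% vs 70% (assumed) | 0.44 | 0.74 | 1.7 |

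At 30% vs 40% the fitted child SD is 4.0, and the maximum is finite: the negative log-likelihood per child is 1.277 at SD 3, 1.267 at SD 4.0 and 1.272 at SD 5.

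**3. With ward effects, simulated trials.** With ward SD 1.0 and fine quadrature (12 trials per scenario), the child-intercept log OR was 2.2 times the ward-only one at 30% vs 40% and 1.7 times at 50% vs 60%. With ward SD 1.18 and 28 children per ward (200 trials, 30% vs 40%), the mean log ORs were 1.234 and 0.586: odds ratios of 3.43 and 1.80, ratio 2.1.

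**4. Is it stronger evidence?** Wald z for arm with 280 children per arm and no ward effect, child-intercept model against M12-only logistic model: 2.41 vs 2.47, 2.35 vs 2.37 and 2.49 vs 2.47 for the three coverage pairs. The coefficient and its standard error grow together.

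**5. Dependence on the fitting method.** On one simulated 30% vs 40% dataset, where the ward-only log OR was 0.52, the written model gave 1.26 by quadrature (child SD 4.1), 0.75 by penalised quasi-likelihood (SD 3.0) and 0.44 by Laplace (SD 10.4). On one 50% vs 60% dataset, quadrature and Laplace agreed (1.40 and 1.41) and penalised quasi-likelihood gave 0.94.

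**6. Adding visit terms.** Once each visit has its own intercept, the monotone sequences can be fitted ever more closely by raising the child variance. At 30% vs 40% (ward effect omitted), with child SD 1, 5, 10 and 15, the log OR is 0.51, 1.39, 2.59 and 3.8, while the negative log-likelihood per child falls from 1.386 to 1.065, 1.031 and 1.025. In simulated trials a standard R mixed-model routine returned child SDs from 5 to 112 and log odds ratios from −2.6 to 58.

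**The case against.** The best defence is that the SAP already discloses most of this. It says that the outcome is irreversible and that "the intra-individual correlation is largely non-identifiable". It ranks the analysis as exploratory and says that it cannot challenge the time-to-event result. It also notes that the end-of-follow-up model has no child random effect. All of that stands. What is not disclosed is that the two odds ratios are on different scales: reduced efficiency suggests imprecision, not a different estimand.

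Four stronger readings are tempting, and the documents do not support them.

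- *The written model has no stable value.* It has a finite maximum under accurate integration. The divergence in step 6 belongs to a model with visit terms, which the SAP does not list. The instability of the written model comes from the unspecified fitting method.
- *The larger odds ratio is a false signal.* Step 4 shows nearly equal z values; this is a change of scale.
- *The log odds ratio always about doubles.* The ratio falls as coverage rises, and with Laplace fitting the inflation can vanish. The 30% is baseline card coverage. Dose 1 or dose 2 falls due during follow-up (3.4.2.1), so the proportion gaining a dose may be higher and the ratio smaller.
- *The SAP rejects the model and then contradicts itself.* SAP 3.4.2 demotes it openly from the main analysis and keeps it as exploratory.

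It is also fair to say that a discrete-time hazard model would largely repeat the Cox analysis, so simply dropping the output is equally defensible.

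**Conclusion.** The point holds, at low severity. The label is wrong by the form of the model, and no simulation is needed to see it: the odds ratio is conditional on ward and child, and it shares a name with one that is conditional on the ward only. The size of the discrepancy, 1.7 to 2.4 times on the log scale, rests on accurate integration, a constant hazard and coverage between 30% vs 40% and 60% vs 70%; only the lowest pair comes from the SAP. Separately, the model as listed cannot show evolution over time, and the obvious repair of adding visit terms gave no usable finite estimate over the range examined. The primary endpoint, the frailty Cox result and the trial's conclusions are unaffected.

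**What to change.** Either delete 3.4.2.4.2, or replace it with a discrete-time hazard model: each child contributes visits up to the first additional dose; complementary log-log link; visit as a factor; arm; ward random intercept; no child random effect. Its coefficient is a ward-conditional hazard ratio, comparable with the main Cox frailty result. As a caution when planning, ln(0.6)/ln(0.7) = 1.43 at 30% vs 40% is a marginal hazard ratio and should not be presented as the ward-conditional value.

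If the current model is kept:

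- label its odds ratio as conditional on ward and child;
- state that it is not comparable with the odds ratio of 3.4.2.4.1;
- name the integration method;
- show evolution over time through the observed proportions by visit and arm. SAP 3.4.2.1 already describes proportions at each visit and SAP 2.2 description by arm, so this needs little more.

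The cost is a wording change, or one exploratory output lost or changed. No new data are needed.

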1.2.2 Endpoints

The primary endpoint is the measles vaccine coverage, defined as the proportion of children aged 12-23 months in the endline survey who have received at least one dose of measles vaccine, as reported on their vaccination card.

The main secondary endpoint is the measles vaccine coverage, defined as the proportion of children aged 6-12 months at inclusion in the longitudinal follow-up survey, who have received at least one additional dose of measles vaccine, as reported on their vaccination card, administered between inclusion and the end of follow-up.

Secondary endpoints:

- Proportion of children with at least one measles vaccines as reported on their vaccination card or by recall.
- Timeliness of measles 1 vaccination (i.e. within 30 days of turning 9 months), as reported on their vaccination card.
- Timeliness of measles 2 vaccination (i.e. within 30 days of turning 15 months), as reported on their vaccination card.
- Proportion of children with each of the following vaccine doses, as reported on their vaccination card or by recall: measles 1, measles 2, pentavalent 1 and 3, yellow fever and meningitis.
- Proportion of children with age-eligible vaccines such as measles 1, measles 2, yellow fever, meningitis, and catch-up vaccines like pentavalent 1 and 3, as reported on a vaccination card or by recall.
- Proportion of zero-dose children as reported on a vaccination card or by recall, two definitions : none dose, and no penta 1 dose.
- Proportion of fully immunized children, i.e. children who received all age-eligible vaccination.
- Anthropometric parameters mean change in children: MUAC, z scores for MUAC for age, weight for age, weight for height, and height for age.
- Proportion of vitamin A dose 1 given at 6 months and dose 2 given at 12 months
- Evolution of aggregate data collected routinely at health facilities, mean and proportion: paediatric curative and preventive consultations, vaccination activities, SQ-LNS activities, activities on vaccination and Infant and Young Child Feeding (IYCF) sensitization, vaccine and SQ-LNS consumption.
- Barriers and facilitators to access health care centres and receive SQ-LNS mass supplementation implemented as a routine preventive program nested in health facilities activities.
- Adherence to SQ-LNS supplementation.
- Barriers and facilitators to vaccination uptake at health facilities activities.

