Proportion of children fully immunized	Children who had received all childhood vaccinations recommended by the Nigeria MOH, by vaccination card or by recall.	Children aged 12-23 months in the cross-sectional endline survey	Proportion	After one year of the SQ-LNS program (measured in the endline HHS)
		Children aged 6-12 months at inclusion in the longitudinal follow-up survey	Time-to-event analysis; cumulative incidence at end of follow-up	Between inclusion and the end of longitudinal follow-up
Anthropometric parameters	MUAC, z scores for MUAC for age, weight for age, weight for height, and height for age	Children aged 6-12 months at inclusion in the longitudinal follow-up survey	Median/mean	End of follow-up
Vitamin A supplementation coverage	Dose 1 given at 6 month and dose 2 given at 12 months by vaccination card or by recall	Children aged 12-23 months in the cross-sectional endline survey	Proportion	After one year of the SQ-LNS program (measured in the endline HHS)
		Children aged 6-12 months at inclusion in the longitudinal follow-up survey	Time-to-event analysis; cumulative incidence at end of follow-up	Between inclusion and the end of longitudinal follow-up

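### The anthropometric model has no visit term and its effect names no visit, so as written it estimates an average over M4, M8 and M12, not the end-of-follow-up effect in Table 1

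*SAP*

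**What the plan says.** Section 1.2.2 lists the endpoint as "Anthropometric parameters mean change in children: MUAC, z scores for MUAC for age, weight for age, weight for height, and height for age", with no timepoint. Table 1 in the same section gives one, "end of follow-up", for children in the longitudinal survey. The secondary objectives in 1.2.1 ask for the effect on anthropometric status after twelve months of the programme. Section 3.4.2.1 places the follow-up visits at M4, M8 and M12.

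Section 3.4.3.1 first plans a description of each parameter, and of its change from baseline, at every visit. It then specifies a linear mixed model with arm as the listed fixed effect, a ward random intercept and a second "random intercept to account for within-individual correlation nested inside ward over time". On the response it says: "This model will be for the change in the endpoint of interest at different timing with baseline value". Further down it adds the child's own baseline value and the cluster baseline mean as adjustments. The intervention effect is one between-arm difference in mean change, with no visit attached. No visit, time or arm-by-visit term appears in the section.

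The repeated binary model in 3.4.2.4.2 also lists arm as its only fixed effect, although the SAP says of it: "This analysis is intended to provide additional insights into the evolution of vaccination probability over time".

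**The concern.** The endpoint table and the model do not describe the same quantity. A model that pools several visits per child, with arm but no visit in the fixed part, returns one coefficient that averages the visit-specific differences. Table 1 asks for the difference at one visit, the last.

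Three things are at stake. The reported effect may be smaller or larger than the endpoint as defined. If children leave follow-up at different rates in the two arms, the arms' means rest on different mixes of visits, and any change over time common to both arms is partly attributed to the intervention. And because no visit is named, the choice between a pooled average and an M12 contrast stays open until the data are seen. Section 3.4.3.1 is the only planned comparative analysis of anthropometry, which is the nutritional half of the hypothesis in 1.1.

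**Working it through.** The SAP gives no effect size, variance or dropout by visit for anthropometry, so there is no planned figure to reproduce. The check has two parts.

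**1. Which reading of 3.4.3.1 is natural?**

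- *One pooled model.* A child intercept intended for correlation over time needs several records per child in the same fit.
- *A separate model per visit.* Each child then has one record, and the child variance cannot be separated from the residual. The SAP applies this logic itself in 3.4.2.4.1, where it leaves out a patient effect because the endpoint is seen only once per child.

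The pooled reading is therefore the natural one. Under either reading, M12 is not named as the effect.

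**2. What does the arm coefficient estimate?**

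From the SAP: visits at M4, M8 and M12; random intercepts for ward and child; arm as a fixed effect. Baseline covariates do not vary by visit and are left out. Assumed: 20 wards of 30 children; SDs of 0.1 (ward), 0.5 (child) and 0.5 (residual); a control-arm trend in change of −0.1, −0.2, −0.3; and the effect patterns below.

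*Complete data.* Every child contributes three visits with equal weight, so the coefficient is (d4 + d8 + d12)/3.

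| Assumed differences at M4, M8, M12 | Arm coefficient | M12 effect | Ratio |
|---|---|---|---|
| 0.1, 0.2, 0.3 (linear growth) | 0.6/3 = 0.20 | 0.30 | 67% |
| 0, 0, 0.3 (late) | 0.3/3 = 0.10 | 0.30 | 33% |
| 0.3, 0.3, 0.3 (constant) | 0.9/3 = 0.30 | 0.30 | 100% |
| 0.3, 0.2, 0.1 (waning) | 0.6/3 = 0.20 | 0.10 | 200% |

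With visit and arm-by-visit terms, the M12 contrast equals the assumed M12 effect in every row.

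*Dropout equal in both arms* (10% last seen at M4, 10% at M8, 80% complete). A child seen n times has weight 1/(0.25 + 0.25/n), which is 2, 2.667 and 3 for n = 1, 2, 3. Under linear growth, the mean difference over the visits such children attend is 0.10, 0.15 and 0.20:

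- numerator: 0.1×2×0.10 + 0.1×2.667×0.15 + 0.8×3×0.20 = 0.02 + 0.04 + 0.48 = 0.54
- denominator: 0.2 + 0.267 + 2.4 = 2.867
- coefficient: 0.54/2.867 = 0.188, against 0.30 at M12

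For the late effect, only completers contribute: 0.8×3×0.10/2.867 = 0.084.

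*Dropout that differs by arm, with no true effect* (control 20%, 20%, 60%; NutriVax 0%, 10%, 90%). The trend gives within-child means of −0.10, −0.15 and −0.20:

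- control: −(0.04 + 0.08 + 0.36)/(0.4 + 0.533 + 1.8) = −0.48/2.733 = −0.1756
- NutriVax: −(0.04 + 0.54)/(0.267 + 2.7) = −0.58/2.967 = −0.1955
- arm coefficient: −0.1955 + 0.1756 = −0.020

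Adding visit as a fixed effect brings this to 0.000. The leak is proportional to the trend and vanishes if there is none.

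**The case against.** The strongest reply is that 3.4.3.1 is incomplete and does not commit to averaging. Its bullet list is plainly not exhaustive, since the two baseline adjustments appear only further down. The response sentence could be read as visit-specific. The endpoint list in 1.2.2 and the opening of 3.4.3.1 speak of mean change without a timepoint, so only the Table 1 entry and the general objective fix the end of follow-up. The change at each visit will also be described, and section 2.2 describes variables by arm.

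Much of this is fair, and it limits the point: the SAP nowhere says that it intends an average. It does not remove the point. The child intercept over time makes pooling the natural reading, the visit-by-visit reading leaves that intercept unidentifiable, and neither reading names M12. The descriptive tables give no modelled contrast that allows for clustering. The general clause about checking assumptions concerns model fit, not which visit the effect belongs to.

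A reader might go further and infer that the model will dilute a benefit that builds up with exposure. The SAP does not support that: it states no effect pattern, and under a waning effect the average exceeds the M12 effect. Nor does it support large time trends. Four of the five parameters are z-scores, and the −0.020 leak rests on an assumed trend and on completion of 60% against 90%.

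A reader might also give the repeated binary model equal weight. It is labelled exploratory, cannot displace the time-to-event result, and already acknowledges limited identifiability, which a visit term would not cure.

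**Conclusion.** The point holds for 3.4.3.1 and should be corrected. Following the listed terms gives a quantity that matches Table 1 only if the effect is the same at all visits and time trends do not leak in through unequal dropout. Under the assumed patterns with complete data, it lies between 33% and 200% of the M12 effect. The direction of the discrepancy cannot be known from the SAP, and the figures illustrate sensitivity; they do not forecast an error. These are secondary endpoints without a sample size calculation of their own, so the primary and main secondary analyses are unaffected. The missing time term in 3.4.2.4.2 is a minor inconsistency with that model's stated aim.

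**What to change.** In 3.4.3.1, add visit (categorical: M4, M8, M12) and arm-by-visit as fixed effects, and define the intervention effect as the adjusted arm difference in change at M12, with M4 and M8 supportive. Alternatively, model the M12 change alone and drop the child intercept; this loses the earlier visits of children not seen at M12. State the end of follow-up in the endpoint list in 1.2.2 as well, so that it agrees with Table 1.

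In 3.4.2.4.2, add visit, or remove the stated aim of showing evolution over time.

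The cost is a few lines of text and code, with no change to data collection, and some precision. Under the variances assumed above and complete data, the variance of a ward mean is 0.01 + 0.50/30 = 0.0267 for the M12 change, and 0.01 + (0.25 + 0.25/3)/30 = 0.0211 for the all-visit average. The standard error is therefore √(0.0267/0.0211) = 1.12 times as large, but it belongs to the quantity that Table 1 asks for.
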